9.1. Schedule of Events

Enrollment/Baseline

Subjects are considered enrolled at the time the study-specific informed consent is signed. Each subject must meet all the inclusion and no exclusion criteria to be eligible to participate in the study. At the enrollment/baseline visits, data will be gathered from subjects including relevant medical and concomitant OAB medication history. Enrollment and Baseline Visit requirements will occur at separate visits.

Subjects will complete the following questionnaire:

- Overactive Bladder Symptoms Quality of Life Questionnaire (ICIQ-OABqol)

The voiding diary will be explained and given to the subject to be completed for 3 consecutive days. The 3-day voiding diary must be completed along with confirmation that the subject is not pregnant or planning to become pregnant during participation in the trial, as part of the assessment for study eligibility.

Any reportable adverse events following informed consent will be documented and reported. Device deficiencies will be collected beginning at the time of the first exposure to the InterStim II System.

Tined Lead or temporary Test Stimulation Lead Implant

If using basic evaluation, the temporary Test Stimulation Lead should be placed in accordance with the InterStim System Test Stimulation Lead Kit and Test Stimulation Lead Technical manual.

If using advanced evaluation, the InterStim tined lead (model 3889) should be placed in accordance with the InterStim Therapy Model 3889 Lead Implant Manual.

[Redacted text block]

[Redacted text block]

[REDACTED]

Settings may be set per Investigator discretion during the therapy evaluation period and will be documented. Any [REDACTED] reportable adverse events/device deficiencies will be documented and reported.

Therapy Evaluation

The therapy evaluation period should be conducted in accordance with the InterStim II System Labeling. The therapy evaluation period must not exceed either 14 days if using InterStim tined lead or 7 days if using the temporary Test Stimulation Lead as defined by current labeling, or a new approved duration in an updated commercially available labeling in the respective country. A 3-day voiding diary will be completed towards the end of the therapy evaluation period. A minimum of a 50% improvement in UUI or UF voiding symptoms, or return to normal voiding of < 8 voids per day for UF subjects, is required in order to qualify for a neurostimulator implant in the study. Settings used during therapy evaluation will be documented during this visit. Any [REDACTED] reportable adverse events/device deficiencies will be documented and reported.

Tined Lead (if applicable) / Neurostimulator Device Implant (randomization procedures)

Once the subject qualifies for the neurostimulator device implant, site personnel may proceed with the neurostimulator device implant and randomization procedures. If a subject does not qualify for the neurostimulator device implant, they will be exited from the study.

For subjects who qualify for device implant following a successful basic evaluation, the InterStim tined lead should be placed in accordance with the InterStim Therapy Model 3889 Lead Implant Manual.

[REDACTED]

At the time of the neurostimulator device implant, site personnel will obtain a randomization assignment to randomize each subject to one of the following therapy amplitudes: sensory threshold, 50% of sensory threshold or 80% of sensory threshold. Subjects are blinded to their randomization. All measures should be taken to ensure that the subject does not become unblinded to their randomization throughout the study.

Subjects will be implanted with the Neurostimulator in accordance with the InterStim Therapy InterStim II Model 3058 Neurostimulator Implant Manual.

After the device implant is complete, it is required that subjects be programmed to 14 hertz (Hz), 210 μ s pulse width (pw) and continuous stimulation for the duration of the study. During programming, the subject's sensory threshold amplitude will be determined by following this protocol: start at 0.05 volts (V) and increase voltage using fine resolution in 0.05 V increments until the subject reports sensation.

Prior to discharge, the amplitude at each electrode configuration that elicits a sensory response must be determined in [REDACTED] seated [REDACTED] positions. To determine sensory threshold, each electrode (0,1,2,3) will be programmed as the cathode (negative) in a bipolar configuration in a systematic fashion.

Following determination of sensory threshold, amplitude will be programmed based on the assigned randomization of sensory threshold, 80% of sensory threshold, or 50% of sensory threshold using the sensory threshold in a seated position. As part of the programming, impedance checks should be completed. Upon completion of programming, data will be collected via a programming printout or Neuro Programmer Upload (NPU).

Subjects will be allowed to adjust amplitude ± 0.05 V during the study. Therapy amplitude will remain at this level (± 0.05 V) until the next follow-up visit or programming session. Any [REDACTED] [REDACTED] reportable adverse events/device deficiencies will be documented and reported.

1-Week Follow-up Visit

At the 1-week follow-up visit, any reportable adverse events, device deficiencies [REDACTED] [REDACTED] will be collected.

During the visit, the subject's sensory threshold amplitude will be captured by following this protocol: start at 0.05 V and increase voltage using fine resolution in 0.05 V increments until the subject reports sensation. Prior to the completion of the visit, the amplitude at each electrode configuration that elicits a sensory response must be determined in [REDACTED] seated [REDACTED] positions. To determine sensory threshold, each electrode (0,1,2,3) will be programmed as the cathode (negative) in a bipolar configuration in a systematic fashion.

Following determination of sensory threshold amplitude, amplitude will be programmed based on the assigned randomization using sensory threshold in a seated position. Subjects will be allowed to adjust amplitude ± 0.05 V during the study. As part of the programming, impedance checks should be completed. Upon completion of programming, data will be collected via a programming printout or NPU.

Over the course of the study any changes to programmed parameters (amplitude, PW, rate or cycling) outside of the allowable settings in the study will be considered a protocol deviation; however, subjects will be encouraged to continue in the study.

The voiding diary will be explained and given to the subject to be completed approximately 3 days prior to the 6-week follow-up visit.

6-Week Follow-up Visit

At the 6-week follow-up visit, the subject's voiding diary completed during the previous period will be collected. [REDACTED] reportable adverse events, device deficiencies and other information will be collected from the subject.

[REDACTED]

[REDACTED]

During the visit, the subject's sensory threshold amplitude will be captured by following this protocol: start at 0.05 V and increase voltage using fine resolution in 0.05 V increments until the subject reports sensation. Prior to the completion of the visit, the amplitude at each electrode configuration that elicits a sensory response must be determined in [REDACTED] seated [REDACTED] positions. To determine sensory threshold, each electrode (0,1,2,3) will be programmed as the cathode (negative) in a bipolar configuration in a systematic fashion.

Following determination of sensory threshold, amplitude will be programmed based on the assigned randomization using the sensory threshold in the seated position. Subjects will be allowed to adjust amplitude +/- 0.05 V during the study. As part of the programming, impedance checks should be completed. Upon completion of programming, data will be collected via a programming printout or NPU.

The voiding diary will be explained and given to the subject to be completed approximately 3 days prior to the 12-week visit.

12-Week Follow-up Visit

At the 12-week follow-up visit, the subject's voiding diary completed during the previous period will be collected. [REDACTED] reportable adverse events, device deficiencies and other information will be collected from the subject. During the visit, the subject's sensory threshold will be captured by following this protocol: start at 0.05 V and increase voltage in 0.05 V increments until the subject reports sensation. Prior to the completion of the visit, the amplitude at each electrode configuration that elicits a sensory response must be determined in [REDACTED] seated [REDACTED] positions. To determine sensory threshold, each electrode (0,1,2,3) will be programmed as the cathode (negative) in a bipolar configuration in a systematic fashion. As part of the programming, impedance checks should be completed. Upon completion of programming, data will be collected via a printout or NPU.

Subjects will complete the following questionnaires:

- ICIQ-OABqol

The subject is exited from the study after the 12-week follow-up visit is complete. Programming parameters after the subject has completed the study are at the Investigator's discretion.

Unscheduled Visit

If an unscheduled visit is needed for any device-related reason, the subject's sensory threshold amplitude will be confirmed by following this protocol: start at 0.05 V and increase voltage in 0.05V increments until the subject reports sensation. Prior to the completion of the study, the amplitude at each electrode configuration that elicits a sensory response must be determined in [REDACTED] seated [REDACTED] [REDACTED] positions. To determine sensory threshold, each electrode (0,1,2,3) will be programmed as the cathode (negative) in a bipolar configuration in a systematic fashion.

Following determination of sensory threshold amplitude, amplitude will be programmed based on the assigned randomization using the sensory threshold in a seated position. Subjects will be allowed to adjust amplitude +/- 0.05 V during the trial. As part of the programming, impedance checks should be completed. Upon completion of programming, data will be collected via a programming printout or NPU.

All efforts should be made to maintain subject in the randomized arm. If the subject must be changed from their randomized arm, subjects should be encouraged to complete a 3-day voiding diary prior to the unscheduled visit.

[figure not shown]
In addition to programming activities, any [REDACTED] reportable adverse events and device deficiencies will be collected.

Surgical Revision

If a surgical revision is required after the full system implant, the subject will be exited from the study.

Figure 9-1: Study Visits illustrates required study visits for basic and advanced evaluations:

Figure 9-1: Study Visits

InterStim Amplitude Clinical Investigation Plan

MDT17030

Version 2.0

Page 29 of 61

Table 9-1: Study Procedures

	Enrollment / Baseline	Tined Lead or Test Stimulation Lead Implant	Therapy Evaluation	Tined Lead (if applicable)/ Neurostimulator Device Implant	1-Week Follow-Up Visit (+/- 3 days)	6-Week Follow-Up Visit (+/- 7 days)	12-Week Follow-Up Visit (+/- 7 days)	Unscheduled Visit
Informed Consent	X*							
Randomization Procedures				X***				
Relevant Medical History	X							
ICIQ-OABqol Questionnaire	X						X	
Pregnancy Assessment	X							
[REDACTED]		[REDACTED]		[REDACTED]				
Assessment of Sensory Threshold		X		X	X	X	X	X
PGI-I Questionnaire						X	X	
3-Day Voiding Diary	X**		X**			X	X	X****
Device Interrogation/ Programming Data		X	X	X	X	X	X	X
[REDACTED]	█	█	█	█	█	█	█	█
Assessment of Reportable Adverse Events and Device Deficiencies	X	X	X	X	X	X	X	X

* Must occur prior to any study specific activities

**50% improvement in UUI or UF voiding symptoms, or return to normal voiding of < 8 voids per day for UF subjects, required for neurostimulator implant

***Randomization must occur after study qualification; however, may be prior to or after neurostimulator device implant

****If the subject must be changed from their randomized arm, subjects should be encouraged to complete a 3-day voiding diary prior to the unscheduled visit.

[REDACTED]

Note: Programming settings of 14 hz, 210 pw and continuous stimulation are required following the neurostimulator device implant for the duration of the study

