6.1. Duration

Study subjects will be enrolled and will complete enrollment and baseline assessments to determine eligibility for an InterStim lead implant procedure. Subjects that do not meet eligibility criteria and/or qualify for a neurostimulator device implant will be exited from the study. All enrolled subjects that qualify for the study (meet all inclusion and no exclusion criteria) will be randomized and undergo an InterStim II device implant procedure. Post implant, subjects will be required to attend the 1-week follow-up visit (window +/- 3 days), 6-week follow-up visit (window +/- 7 days), and 12-week follow-up visit (window +/- 7 days). The visits are expected to occur over approximately 16 weeks starting at the enrollment visit.

The estimated study duration, from first subject enrollment to last subject visit, is expected to last approximately 18 months. The completion of the study is defined as the approval of the Final Study Report and closure of all sites.

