9.5. Randomization and Treatment Assignment

Once the subject meets all eligibility criteria for the study, and has a successful therapy evaluation, site personnel may proceed with the neurostimulator device implant and randomization procedures. If a subject does not meet all eligibility criteria, subjects should be exited and not proceed to the neurostimulator device implant and randomization procedures.

At the time of the device implant, site personnel will obtain randomization for one of the following therapy amplitudes: sensory threshold, 50% of sensory threshold or 80% of sensory threshold. Randomization will be assigned in a 1:1:1 ratio, and stratified by site. Site personnel will obtain the subject's randomization sequence on the Randomization eCRF which will be generated from the database.

The investigator and research staff at the study site will be instructed to keep the subject blinded to their randomization; however, subjects may or may not feel stimulation. The outcome measures in this study are based on the subject's own assessment. Therefore, keeping the subject blinded to their randomization reduces bias in the outcome measurement reporting. [REDACTED]

During the study, subjects will be encouraged to remain in the randomized treatment arm; however, a subject may request to be re-programmed with a different amplitude setting. If this occurs, a protocol deviation will be required and subjects should continue in the study and complete the remaining follow-up visits.

[REDACTED]

[REDACTED]

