13.4 Additional Measures

Additional measures have been added to provide relevant information on parameters of interest in SNM therapy under different amplitude settings and to provide additional information.

Additional measures to summarize are:

- Incidence of device-related, procedure-related and/or therapy-related adverse events

█ [REDACTED]

█ [REDACTED]

Reportable device-related, procedure-related and/or therapy-related adverse events will be summarized for subjects who are implanted and randomized under each amplitude setting. Device-deficiencies will be summarized in the similar fashion. In addition, serious adverse events will be summarized.

█ [REDACTED]

█ [REDACTED]

█ [REDACTED]

14. Ethics

14.1.Statement(s) of Compliance

The study will be conducted in accordance with this protocol, the ethical principles that have their origin in the Declaration of Helsinki have been implemented in this clinical study by means of the informed consent process, EC/IRB approval, study training, and risk benefit assessment. In addition, all applicable laws and regulatory requirements of the country/ies in which the study is conducted will be followed and in accordance with GCP.

- In the US, the study will be conducted in accordance with 21 CFR§11 Electronic Records, Electronic Signatures, 21CFR§50 Protection of Human Subjects, 21CFR§56 IRB, and 21CFR§803 Medical Device Reporting. Financial disclosures will be collected; however, this study is not considered a “covered study” under 21 CFR§54 Financial Disclosure by Clinical Investigators.
- In Europe, the study will be conducted in accordance with regional or national regulations, as appropriate.
- In Canada, the study will be conducted in accordance with Canada Medical Devices Regulations, 1998 (SOR/98-282), and the Guidance document for Mandatory Problem Reporting.

Any additional requirements imposed by the IRB/EC or governing regulatory authority shall be followed, if appropriate.

Medtronic will distribute the approved version of the CIP and all other materials required to conduct the study. Prior to site activation, Medtronic will provide study training relevant and pertinent to the involvement of personnel conducting study activities and investigator responsibilities. Medtronic will not activate any site until the required approval/favorable opinion from the Institutional Review Board (IRB)/Ethics Committee (EC) or notification/approval from a regulatory authority have been obtained, if appropriate.

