### 7.10.7.3. Post-Neurostimulator Device Implant

Events that have an onset date on or after the day of the neurostimulator implant procedure will be summarized as Post-Neurostimulator Device Implant Events. Events that occur post-neurostimulator device implant will be summarized by randomization group [REDACTED]

[REDACTED] The [REDACTED] denominator for the summary by randomization group will be the randomized subject set.

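### Randomisation may precede implant, so unblinded staff can know the arm during permanent lead placement (basic evaluation only), electrode choice and the first post-implant threshold test; the post-implant safety denominator is also stated inconsistently

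*Protocol*

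**What the plan says.** **Timing.** The three-asterisk footnote to Table 9-1 reads: "Randomization must occur after study qualification; however, may be prior to or after neurostimulator device implant". The body of Protocol 9.1 ties it to the implant visit: "At the time of the neurostimulator device implant, site personnel will obtain a randomization assignment to randomize each subject". Section 9.5 says much the same. Section 6.1 names randomisation first, saying that qualifying subjects "will be randomized and undergo an InterStim II device implant procedure". No visible text places the assignment after the post-implant threshold reading.

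**Who knows the arm.** Protocol 9.5: "Site personnel will obtain the subject's randomization sequence on the Randomization eCRF". The same section says "The investigator and research staff at the study site will be instructed to keep the subject blinded to their randomization". The design is single-blind, and the staff who implant and program are not described as masked.

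**Threshold.** Under Protocol 9.1 staff begin at 0.05 V and "increase voltage using fine resolution in 0.05 V increments until the subject reports sensation". Each of the four electrodes is tested as cathode. The amplitude is then programmed at 100%, 80% or 50% of the seated threshold. The test is repeated, and the amplitude reset, at 1 and 6 weeks.

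**Safety denominator.** SAP 7.10.7.3 counts events from the day of implant onward and says the "denominator for the summary by randomization group will be the randomized subject set". SAP 7.9.3.1 uses the same set, and SAP 7.1.3 defines it as everyone randomised. Protocol 13.4 says related events "will be summarized for subjects who are implanted and randomized under each amplitude setting". The opening of SAP 7.10 refers to the number of subjects in each phase.

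**The concern.** The seated threshold is the unit in which all three arms are expressed, and lead position and electrode configuration determine what that threshold is. If the operator knows the arm while these are being fixed, they can differ between arms for reasons other than chance, and randomisation gives no protection against differences that arise after assignment.

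Lead placement deserves most weight. After basic evaluation, the permanent tined lead goes in at the same visit as the neurostimulator. Protocol 9.1 exits any subject who needs surgical revision after full implant, so everyone who reaches the 12-week diary does so with the lead as first placed. Later visits can re-test thresholds but cannot undo placement.

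Early assignment also allows a subject to be randomised and never implanted. Such a subject cannot have a post-implant event, yet counts in the SAP's denominator for those events.

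**Working it through.** **1. What can happen with the arm known.** The order of steps at the implant visit, from Protocol 9.1 and Table 9-1:

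- *Tined lead, advanced evaluation:* placed before the therapy evaluation, hence before qualification and randomisation. Not exposed.
- *Tined lead, basic evaluation:* placed after qualification, at the implant visit. Exposed if the assignment is obtained first.
- *Threshold at the lead implant visit:* marked in Table 9-1, before randomisation. Not exposed; in basic-evaluation subjects it is taken on the temporary lead.
- *First post-implant seated threshold and electrode configuration:* exposed unless the assignment is obtained afterwards. Randomising after implant does not by itself guarantee this. The visible text gives no rule for choosing the therapy configuration from those tested.
- *1- and 6-week thresholds:* always taken after randomisation by staff who can know the arm.

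The assignment is not needed until the amplitude is programmed, which Protocol 9.1 places after the threshold has been determined.

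**2. How much one ramp step matters.** The documents give no threshold values. Assume a threshold T between 0.25 and 2.0 V. One step as a share of T is 0.05/T. The gap between the 80% and 100% arms, in steps, is 0.20 × T/0.05.

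| Assumed T (V) | One step as % of T | 80% to 100% gap, in steps |
|---|---|---|
| 0.25 | 20 | 1 |
| 0.5 | 10 | 2 |
| 1.0 | 5 | 4 |
| 2.0 | 2.5 | 8 |

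This shows sensitivity to a one-step difference. It does not estimate a bias, and the documents support no size or direction for one.

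**3. Arm size.** Protocol 13.1.1 and SAP 6 plan 42 completers, 10% attrition after full implant and 80% therapy evaluation success. 42/0.90 = 46.7, rounded up to 47, against a stated figure of about 48. 48/0.80 = 60, as stated in SAP 6. With 1:1:1 allocation, 48/3 = 16 per arm. These figures reproduce to within rounding, and nothing here changes them.

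**4. Denominator.** Let e be subjects with an event and k subjects randomised but never implanted, in an assumed arm of 16. The SAP reports e/16; Protocol 13.4 implies e/(16 − k). The ratio is (16 − k)/16, so the relative dilution is k/16.

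- k = 0: no difference.
- k = 1: 1/16 = 6.25%. With e = 4, 4/16 = 25.0% against 4/15 = 26.7%.
- k = 2: 2/16 = 12.5%. With e = 4, 25.0% against 4/14 = 28.6%.

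The documents give no expected k. The three denominator statements agree only when k = 0, which the footnote does not ensure.

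**The case against.** The strongest reply is that the proposed change protects little of the primary endpoint. Thresholds are re-read and amplitudes reset at 1 and 6 weeks with the arm known. The first post-implant reading therefore governs roughly one of the 12 weeks, and, absent an unscheduled reprogramming, the amplitude in force during the 12-week diary comes from the 6-week reading. This stands for the threshold test. It does not answer the lead-placement point, because no later visit revisits placement.

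A reader might infer that staff can set the threshold to suit the arm. The documents do not support that: start, step and stopping rule are fixed, and the stop is the blinded subject's report. What remains is the manner of conducting the test and the choice of configuration. One step also equals the ±0.05 V adjustment allowed to subjects.

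A reader might also infer that lead placement is exposed in every subject, or that the reading in question is the first of any kind. Neither is so: advanced-evaluation leads precede randomisation, and Table 9-1 marks an earlier threshold assessment.

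The objectives are descriptive, with no hypothesis tests (SAP 7.2.1) and a sample the protocol synopsis calls too small to compare arms. That limits the consequence. The arm summaries will still be read side by side.

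On the denominator, the plan treats implanted and randomised as the same 48 or so subjects, so k should be small. That also stands. Finally, text is redacted in Protocol 9.1 at the implant procedure, in 9.5 after the blinding paragraph, and in SAP 7.10.7.3 beside the denominator sentence. A relevant safeguard there cannot be excluded.

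**Conclusion.** The point holds in limited form. The visible text lets unblinded staff know the arm during permanent lead placement after basic evaluation, during the initial electrode choice, and during the first post-implant, dose-defining threshold test. The size of any resulting bias cannot be derived. The case for change is that the path is avoidable at very low cost and, for lead placement, cannot be corrected later.

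It would be wrong to conclude that later assignment makes dose-setting blind: the 1- and 6-week readings stay unblinded.

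The denominator conflict is real but small: about 6% relative dilution per never-implanted subject, assuming 16 per arm. It affects descriptive adverse-event percentages only. The primary analysis uses complete cases with baseline and follow-up data and is not affected.

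Both conclusions assume that the redacted passages contain no further rule on timing, masking or denominators.

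**What to change.** Reword the Table 9-1 footnote and Protocol 9.5 so that the Randomization eCRF releases the assignment only after site staff confirm two things: the implant is complete, and the first post-implant seated thresholds and electrode configuration have been recorded. Bring the timing wording in Protocol 6.1 and 9.1 into line.

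In SAP 7.9.3.1 and 7.10.7.3, use implanted and randomised subjects as the denominator for post-implant event percentages, as Protocol 13.4 does, and make the opening of SAP 7.10 agree. With the assignment released after implant, randomised but never-implanted subjects should largely disappear.

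The cost is a few sentences, an eCRF release check and one SAP wording change. The operational burden is more than an edit check: programming data are otherwise collected once programming is finished, so sites must make a short confirmation mid-visit, and the assignment arrives later in that visit. No new visit, procedure or staff is needed. A side benefit is one threshold on the permanent lead, recorded before allocation, against which the later unblinded readings can be described by arm.
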